#### 1.2.9 Previous Human Experience with an Extracellular/Transmembrane/Intracellular HER2/neu Vaccine

Our collaborator [name], and his colleagues at the Karolinska Institute in Sweden have conducted a pilot clinical trial of a plasmid DNA human HER2/neu vaccine encoding the extracellular (EC), transmembrane (TM) and mutated intracellular (ICmutated) domains (ECTMICmutated) given with GM-CSF and IL-2. As a safety measure, a two base pair mutation was introduced in the IC domain to remove an autophosphorylation site that confers oncogenicity and maximize safety. The vaccine was administered to a total of eight patients and no clinical issues of acute toxicity, autoimmunity or cardio toxicity were identified. As might be expected with a DNA plasmid construct, the vaccine demonstrated limited immunogenicity: no specific T-cell proliferation following *in vitro* stimulation of *ex vivo* PBMCs with recombinant human HER2 protein was induced by vaccination. In fact, immediately following three complete cycles of vaccination, no or even decreased HER2-specific CD4+ T-cell responses were observed, but a significant increase in MHC class II restricted HER2-T-cell responses was detected at long term follow-up. Because concurrent trastuzumab therapy was permitted during the study,  $\lambda$ -subclass specific ELISAs were performed to measure endogenous antibody production without trastuzumab interference. Importantly, in a subgroup of patients, HER2-pDNA vaccination induced and boosted HER2-specific antibodies that could be detected for several years following the last vaccine administration.

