### 3.1.1 Dose Limiting Toxicity

The following assessment guidelines for the management of dose limiting toxicity (DLT) are intended to ensure the safety of each patient while on the study. The descriptions and grading scales found in the revised NCI Common Terminology Criteria for Adverse Events (CTCAE) version 4.0 will be utilized for AE and DLT reporting. All appropriate treatment areas should have access to a copy of the CTCAE version 4.0. A copy of the CTCAE version 4.0 can be downloaded from the CTEP web site ([http://ctep.cancer.gov/protocolDevelopment/electronic\\_applications/ctc.htm#ctc\\_40](http://ctep.cancer.gov/protocolDevelopment/electronic_applications/ctc.htm#ctc_40)).

All adverse events will be classified as follows for determination of relatedness to AdHER2 vaccination:

- Unrelated
- Unlikely
- Possibly related
- Probably related
- Definitely related

For the purposes of this study, the definitions of dose limiting-toxicities include:

- CTCAE Grade 2 and greater allergic reactions
- CTCAE Grade 2 and greater autoimmune disorders
- CTRCD, defined as a decrease in the LVEF of > 10 percentage points, to a value in < 53%. Documentation of the above specified change in LVEF will require cardiac consultation for determination of clinical significance. Cardiac function deterioration clinically associated with apparent cardiotoxic agent use after off-therapy will be censored at the point of cardiotoxic agent use.
- CTCAE Grade 3 or greater organ toxicity (dermatologic, gastrointestinal, hepatic, pulmonary, renal/genitourinary, or neurologic) occurring within 30 days of vaccine administration that are at least possibly related to research in.

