- All patients will be given an AdHER2 DC Vaccine Report Card (refer to [Appendix 5](#)) and instructed on how to complete it, following each AdHER2 DC vaccine dose.
- Continued injection of the same forearm is permissible for patients who have one functional forearm or a medical condition that does not allow for continued injections of both forearms.

Since this protocol involves AdHER2 DC vaccination in humans using this vector for the first time, enrollment into subsequent dose level for both Part I and Part II patients will be staggered to allow for safety monitoring as outlined in Section [3.1.2](#): dose escalation will proceed as long as 0 of 6 or 1 of 6 patients within a dose level have no evidence of toxicity and at least 3 of the 6 patients within the same dose level have reached Week 12 on study before enrollment in the next vaccine dose level can begin. If no dose limiting toxicities as defined in Section [3.1.1](#) are observed in the twelve-week window inclusive of the first three vaccinations, enrollment of additional patients may proceed as quickly as is logistically feasible as outlined above and in accordance with the dose escalation parameters outlined in Section [3.1.2](#).

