 Dose can be delayed up to 8 weeks. The study will reset at the time of study resumption. For example, if dose at week 8 is delayed and resumed at original week 11, that week 11 will now be considered week 8.

 If there is a need for confirmatory scans based on the result of Week 48 evaluation, additional visit will occur at week 52 which will include clinical assessment with physical exam and laboratory assessment.

 Patients who progress do not require a full evaluation. Only physical exam, clinical labs, echocardiogram and AE reports will be required.

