Document AEs from the first study intervention, Study Week 0, through 30 days after the last study intervention. Beyond 30 days after the last study intervention, only adverse events which are serious and related to the study intervention need to be recorded.

An abnormal laboratory value will be considered an AE if the laboratory abnormality is characterized by any of the following:

- Results in discontinuation from the study
- Is associated with clinical signs or symptoms

- Requires treatment or any other therapeutic intervention
- Is associated with death or another serious adverse event, including hospitalization.
- Is judged by the Investigator to be of significant clinical impact
- If any abnormal laboratory result is considered clinically significant, the investigator will provide details about the action taken with respect to the test drug and about the patient's outcome.

Laboratory and clinical symptom abnormalities less than or equal to Grade 1 will not be graded or assessed for attribution to AdHER2 DC vaccine.

**End of study procedures:** Data will be stored according to HHS, FDA regulations and NIH Intramural Records Retention Schedule as applicable.

**Loss or destruction of data:** Should we become aware that a major breach in our plan to protect subject confidentiality and trial data has occurred, this will be reported expeditiously per requirements in Section [7.2.1](#).

[name] will continue to have access to the data for purposes of data analysis and publication. The necessary data will be sent via encrypted email.

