## **12.5 RISKS/BENEFITS ANALYSIS**

Subjects (including subjects unable to give consent) undergoing therapeutic autologous AdHER2 DC vaccination are likely to experience local injection site reactions commonly associated with the delivery of all vaccines i.e. discomfort, itching, redness, swelling, and/or soreness/pain at the injection site. The potential for adverse systemic symptoms such as fatigue, malaise, fever or acute allergic reactions is unknown but is less likely because patients are being given their own cells. However, because patients are being given their own cells as well as a "self" tumor

antigen (HER2), there is the potential for inducing antibodies that react with the patient's own tissues resulting in autoimmune disease. This has not been described with other HER2 vaccines that have been studied but patients will be monitored for the development of autoimmune disease.

The greatest concern associated with this therapeutic vaccine platform is the potential development of vaccine-induced antibodies that result in cardiac dysfunction and toxicity. Unlike trastuzumab, where therapy can be withdrawn, there is no way to "turn off" the immune system without significant adverse consequences. Because of this, cardiac function will be monitored very closely while receiving the vaccine treatment and for 24 months following the last dose of vaccine. In addition, stringent stopping rules are in place in the event of any early (or even late) signals of cardiac toxicity.

The patients eligible to enroll in Part I of this study have recurrent or progressive metastatic disease as well as adjuvant bladder cancer patients with HER2 expressing tumors or naïve to HER2 targeted therapies that are not candidates for currently available HER2-directed therapies such as trastuzumab and lapatinib. Thus, therapeutic vaccination with the AdHER2 DC vaccine platform proposed in this study may result in the development of polyclonal antibodies that successfully target and interfere with HER2 expressed at lower levels and on tumors other than breast cancer and provide a potential direct benefit.

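### Required recording of non-serious adverse events ends 30 days after the last vaccine, but the Grade 2 autoimmune DLT has no time limit, so late autoimmune toxicity can be understated

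*Combined protocol and SAP*

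**What the plan says.** Section 6.1 sets the full recording period: "Document AEs from the first study intervention, Study Week 0, through 30 days after the last study intervention". After that the requirement narrows: "Beyond 30 days after the last study intervention, only adverse events which are serious and related to the study intervention need to be recorded". Both conditions must be met, so a late event that is serious but judged unrelated also falls outside it. Section 8.2 sends the reader back to Section 6.1 for the recording timeframe.

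Section 3.1.1 lists among the DLTs "CTCAE Grade 2 and greater autoimmune disorders". That item carries no time window and no condition on seriousness or relatedness. The Grade 3 organ-toxicity item in the same list does carry them, being limited to events "occurring within 30 days of vaccine administration that are at least possibly related to research in".

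Section 12.5 recognises that the induced antibodies might react with the patient's own tissues and states that "patients will be monitored for the development of autoimmune disease", with no end date. Footnote 18 to the Section 3.4 calendar, which covers Weeks 60 to 124, says of patients who have progressed: "Only physical exam, clinical labs, echocardiogram and AE reports will be required". Section 3.1.2 makes the assessment of the biologically optimal dose conditional on no DLT having been observed.

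**The concern.** The first primary objective in Section 1.1.1 is safety and toxicity in general, with cardiac dysfunction as its specific measure. The product is meant to raise antibody against a self antigen, and Section 3.3 stresses that such a response cannot simply be reversed if it does harm. Yet the period of full recording closes 30 days after dosing stops. From then on, relatedness is a precondition for an event being recorded at all, in an open-label, non-randomized study where the investigators make the attribution.

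Two things are at stake. First, the reported frequency of autoimmune events would be low by rule for late onsets, and an empty table after 30 days could not be read as evidence that none occurred. Second, the no-DLT condition in Section 3.1.2 depends on DLTs that the plan does not require anyone to write down.

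**Working it through.** **Inputs**
- Doses at Weeks 0, 4, 8, 16 and 24 (Section 3.1).
- Full recording to 30 days after the last intervention (Section 6.1), taken here as the last vaccine dose: 30/7 = 4.29 weeks.
- 48 weeks for the primary endpoints, with extended follow-up to monitor LVEF (Précis, Study Design).
- Last scheduled visit at Week 124 (Section 3.4).

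**Length of the gap.** With last dose at week L, full recording ends at E = L + 30/7. The uncovered share of a period of T weeks is (T − E)/T.

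| Last dose | E | Uncovered of 48 weeks | Uncovered of 124 weeks |
|---|---|---|---|
| Week 24 | 28.3 | 48 − 28.3 = 19.7 (41%) | 124 − 28.3 = 95.7 (77%) |
| Week 8 | 12.3 | 48 − 12.3 = 35.7 (74%) | 124 − 12.3 = 111.7 (90%) |

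The 48-week column is the relevant one for primary evaluation. The 124-week column describes follow-up that the plan justifies for LVEF.

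**Does any figure in the plan depend on this?** The plan gives no figure for autoimmune events. Its design probabilities were recomputed with exact binomial formulas, and all reproduce to within 2 percentage points:
- 2 or more of 12: 4.86% and 55.65% (stated 4.9% and 55.7%)
- 2 or more of 18: 10.0% and 77.6% (stated 10% and 78%)
- 2 or more of 24: 16.1% and 89.4% (stated 16% and 89%)
- 3 or more of 30: 6.0% and 84.9% (stated 6% and 85%)

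The 0-of-20 and 0-to-2-of-10 figures also reproduce within that margin. Every one counts cardiac toxicity; none uses autoimmune DLTs.

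**What under-recording could do (illustration only).** Let p be the true per-patient rate of Grade 2 or higher autoimmune disorder. Let f be the share of events that start late, need not be recorded, and in fact go unrecorded. Among 30 patients, the planned size of each Part, the chance of recording at least one is 1 − [1 − p(1 − f)]^30. Both p and f are assumptions; the documents give neither.

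| p | f = 0 | f = 25% | f = 50% | f = 75% |
|---|---|---|---|---|
| 5% | 78.5% | 68.2% | 53.2% | 31.4% |
| 10% | 95.8% | 90.4% | 78.5% | 53.2% |

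For example, p = 10% and f = 50% gives 1 − 0.95^30 = 78.5%.

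**The case against.** A reader might infer that late autoimmunity drops out of the primary safety endpoint. The documents do not support that. The safety measure with statistical rules is cardiac toxicity (Sections 1.1.1 and 11). Escalation, the MTD and the accrual-stopping rules count cardiac toxicity, plus vaccine-related death for stopping. Cardiac toxicity is measured by scheduled echocardiograms to Week 124, independently of the adverse-event window.

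Nor does late autoimmunity vanish altogether. Serious related events are still recorded, and Section 8.1.2 lets medical judgement classify important events as serious. Section 6.1 sets a minimum, and late visits still include examination and laboratory tests, so findings may be noticed. What is lost is the obligation to enter them as adverse events.

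Other fair points:
- DLTs mainly stop a patient's vaccination and gate enrolment, and neither use needs late data. Section 3.2 says that if no DLTs "are observed in the twelve-week window inclusive of the first three vaccinations, enrollment of additional patients may proceed as quickly as is logistically feasible". A patient who receives the Week 8 dose on schedule is fully recorded to at least Week 12.3. Only someone who stops after the Week 0 or Week 4 dose leaves full recording inside that window (Week 4.3 or 8.3).
- Footnote 18 need not contradict Section 6.1. Because Section 8.2 defers to 6.1, the late reports can be read as those that 6.1 requires. The wording is loose rather than clearly in conflict.
- Section 1.2.9 reports "antibodies that could be detected for several years following the last vaccine administration", but for a different product, a plasmid DNA vaccine, in a subgroup of eight patients with no autoimmunity issue identified. Section 12.5 adds that autoimmune disease has not been described with other HER2 vaccines.

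These points narrow the finding. What remains is that an event meeting the plan's own DLT definition need not be recorded, and that Section 3.1.2 relies on the absence of such events without limiting that to the first twelve weeks.

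**Conclusion.** The point holds as a gap between the DLT definition and the recording rule. For a fully dosed patient it covers 19.7 of the 48 primary-evaluation weeks (41%). The 77% figure applies only to the longer LVEF follow-up and should not be the headline. The gap can understate late autoimmune toxicity under the general safety objective and leaves the no-DLT condition unverifiable for late events. It leaves the cardiac endpoint, its stopping rules, the sample size and every stated probability unchanged.

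The percentages assume on-schedule dosing and full follow-up. They are shares of calendar time, not of risk, so they do not estimate the size of any bias. That onset could be late is an inference from the plan's own reasoning in Section 3.3 that the immune response cannot be turned off. The documents give no late autoimmune rate. The calendar's adverse-event row is not relied on, because the table may have been damaged in extraction.

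**What to change.** In Section 6.1, keep the 30-day limit for general non-serious events. Add that Grade 2 or higher autoimmune events are recorded regardless of seriousness or attribution at visits already scheduled, through Week 48 at least and to Week 124 while the patient remains on study. List any intervening therapy beside each late event, and report events up to and after 30 days from the last dose separately.

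Reconcile Sections 3.1.1, 3.4 (footnote 18), 6.1 and 12.5 so that the observation period for the autoimmune DLT is stated and matches the recording period.

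The cost is about one sentence in Section 6.1, matching edits elsewhere and a case-report-form setting. No visits or patients are added, since the late visits already include physical examination and clinical laboratory tests. The downside is that some late events caused by later therapies will be captured, which is why those therapies need to be listed.

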## 6.2 RESPONSE CRITERIA

Tumor measurements for response will be conducted at Weeks 8, 16, 24, 36, 48, 76, 100, and 124 with confirmatory scans obtained not less than 4 weeks following initial documentation of objective response. Adjuvant bladder cancer patients will undergo re-staging at Weeks 8, 16, 24, 36, 48, 76, 100, and 124 with confirmatory scans with confirmatory scans obtained not less than 4 weeks following initial documentation of objective response as outlined in the protocol Study Calendar in Section [3.4](#) and clinical evaluations will include physical examination, neck (optional), chest, abdomen and pelvis CT imaging and bone scan when clinically indicated.

Dependent on the tumor site, MRI can be performed instead of CT scan. Patients with history of CNS disease will be evaluated for the necessity of follow up brain MRI. Due to the requirement of confirmational scans for the evaluation of the response at least 4 weeks after the initial documentation of the response, subsequent scan schedules can be adjusted to allow adequate interval and to avoid unnecessary radiation exposure from fixed CT scan schedules. After off-therapy or PD documentation, restaging scans are optional.

A modified Immune-Related Response Criteria (modified irRC) based on RECIST 1.1 will be used to determine the response as outlined in Section [6.2.6 Table 2](#) [37](#). Changes in the largest diameter (unidimensional measurement) of the tumor lesions and the shortest diameter in the case of malignant lymph nodes will be used as per RECIST 1.1 criteria.

The modified irRC will be based upon RECIST 1.1 criteria (described below) except for 2 major changes:

- 1) require confirmation of progression by imaging at least 4 weeks after initial imaging and
- 2) do not necessarily score the appearance of new lesions as progressive disease if the sum of lesion diameters of target lesions (minimum of 10 mm per lesion, maximum of 5 target lesions, maximum of 2 per organ) and measurable new lesions does not increase by  $\geq 20\%$ .

Efficacy assessments will be made by the Investigator at the investigational site. All objective responses will have confirmatory scans performed at least 4 weeks after the response was first

documented per the modified irRC convention (e.g. initial scan at Week 8, confirmatory scan at Week 12 or after etc.). The PI will review and confirm all objective responses.

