**Table 2 Comparison of RECIST v1.1, modified irRC and iRECIST**

Category	RECIST v1.1	Modified irRC	iRECIST
Measurement of tumor burden	Unidimensional	Unidimensional	Unidimensional
Target lesions	Maximum 5	Maximum 15	Maximum 5
New lesion	Results in progressive disease at first appearance	Does not always results in progressive disease at first appearance unless the sum of tumor burden fits the criteria for progressive disease	
Complete response	Disappearance of all target and nontarget lesions Lymph nodes must regress to <10 mm short axis No new lesions, confirmation required		
Partial response	≥ 30% decrease in tumor burden compared with baseline	≥ 30% decrease in tumor burden compared with baseline† Confirmation required	≥ 30% decrease in tumor burden compared with baseline
Progressive disease	≥ 20% + 5-mm absolute increase in tumor burden compared with nadir. Appearance of new lesions or progression of nontarget lesions	≥ 20% increase in tumor burden compared with baseline, with nadir, or reset baseline. New lesions added to the tumor burden Confirmation required	≥ 20% + 5-mm absolute increase in tumor burden compared with nadir. Appearance of new lesions or progression of nontarget lesions. Confirmation required
Stable disease	Neither partial response nor progressive disease		

For Patients with Measurable Disease (i.e., Target Disease)

Target Lesions	Non-Target Lesions	New Lesions	Overall Response	Best Overall Response when Confirmation is Required*
CR	CR	No	CR	≥4 wks. Confirmation**
CR	Non-CR/Non-PD	No	PR	
CR	Not evaluated	No	PR	≥4 wks. Confirmation**

PR	Non-CR/Non-PD/not evaluated	No	PR	
SD	Non-CR/Non-PD/not evaluated	No	SD	Documented at least once $\geq 4$ wks. from baseline**
PD	Any	Yes or No	PD	no prior SD, PR or CR
Any	PD** *	Yes or No	PD	
Any	Any	Yes	PD	

* See RECIST 1.1 manuscript for further details on what is evidence of a new lesion.
 
** Only for non-randomized trials with response as primary endpoint.
 
*** In exceptional circumstances, unequivocal progression in non-target lesions may be accepted as disease progression.
 
Note: Patients with a global deterioration of health status requiring discontinuation of treatment without objective evidence of disease progression at that time should be reported as "symptomatic deterioration." Every effort should be made to document the objective progression even after discontinuation of treatment.
				

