#### 6.2.7 Confirmatory Measurement/Duration of Response

Confirmation: To be assigned a status of a response of CR or PR, changes in tumor measurements must be confirmed by repeat assessments that should be performed at least 4 weeks after the criteria for response are first met. PD must be confirmed by a second observation no less than 4 weeks later.

Duration of overall response: The duration of overall response is measured from the time measurement criteria are met for CR or PR (whichever is first recorded) until the first date that PD is objectively documented.

The duration of overall CR is measured from the time measurement criteria are first met for CR until the first date that recurrent disease is objectively documented. Time to progression (TTP) will also be recorded for patients with CR, PR and SD subsequently developing recurrent or progressive disease.

**Duration of stable disease:** SD is measured from the start of the treatment until the PD criteria for progression are met.

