Since 0 of 20 patients already have been documented to have NO cardiac toxicity, and 0 to 2 patients out of 30 would have been acceptable per the original study design, a statistical estimate was performed to determine what the probability of having 0 to 2 of the next 10 patients in the Part 1 Expansion Cohort having cardiac toxicity would be. If the probability of cardiac toxicity were 2%, there would be 99.91% probability of 0 to 2 of 10 with toxicity; if it were 5%, there would be 98.8% probability; and if it were 10%, there would be 93% probability of 0 to 2 of 10 with toxicity. Thus, assuming the next 10 patients would have the same underlying per-patient probability of developing cardiac toxicity as the first 20 had, and it is likely to truly be at or below 10%, there is between a 93% and 99.9% probability that the next 10 patients enrolled in the Part I Expansion Cohort would have 0 – 2 toxicities and therefore 0 – 2 of 30 would have cardiac toxicity as per the original study design. Consequently, FDA approval was received on 12/14/15 to initiate enrollment in Part II of the study in parallel, while enrollment of the Part I Expansion Cohort is completed.

The fraction of subjects with immunogenicity, defined as a 3-fold increase in anti-HER2/neu antibody concentration (measured as mcg/mL) or a 4-fold increase in antibody dilution titers over baseline will be reported, along with 80% and 95% confidence intervals, at the following time points: Weeks 4 (after 1 vaccine dose), 8 (after 2 vaccine doses), 12 (after 3 vaccine doses), 28 (after 5 vaccine doses), 48 and 52 weeks and during extended follow-up for monitoring of cardiac adverse events at weeks 76, 100 and 124.

Finally, as a secondary objective, the fraction of subjects who have stable disease, an objective partial response or better by modified irRC will be determined along with appropriate confidence intervals with exceptions to the PR assessment at Week 12 as noted in Sections [3.5.1](#), [3.5.2](#) and [6.2.4](#). The fraction identified in this trial will potentially be useful information for design of any subsequent trials using this vaccine in both of the patient populations being studied.

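### Progression counts only if a second scan confirms it, but that scan is not required, and the plan gives conflicting categories for a first-scan progressor who is never rescanned

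*Combined protocol and SAP*

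**What the plan says.** Section 6.2 scores response by a modified irRC and refers to Table 2 in Section 6.2.6 for the details. The first of its two departures from RECIST 1.1 is to "require confirmation of progression by imaging at least 4 weeks after initial imaging". Section 6.2.7 repeats the rule: "PD must be confirmed by a second observation no less than 4 weeks later".

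Section 6.2 also says: "After off-therapy or PD documentation, restaging scans are optional". For responses the second scan is an obligation: "All objective responses will have confirmatory scans performed at least 4 weeks after the response was first" documented. There is no matching sentence for progression. From Week 60 on, footnote 18 of the Study Calendar (Section 3.4) adds: "Patients who progress do not require a full evaluation". The assessments it then lists do not include a scan.

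Section 3.5.1.2 makes progression a reason to leave therapy. The exception is clinically stable patients with PD at Week 8, 16 or 24, who may stay on at the investigator's discretion.

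The activity endpoint in Section 11.3 is "the fraction of subjects who have stable disease, an objective partial response or better" by modified irRC, with confidence intervals. No denominator is named, and nothing is said about a missing confirmatory scan.

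**The concern.** A rule that needs two scans before a patient counts as a failure works only if the second scan is obtained, or if the plan says what happens when it is not. Here neither holds.

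The missing scans are also unlikely to be random. Section 3.5.1.2 keeps only clinically stable progressors on therapy, and Section 3.5.3.5 takes patients too ill to return off study. The patients doing worst are therefore the least likely to have a second scan. That is an inference from the design, but a reasonable one.

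If these patients are counted as SD they enter the numerator. If they are treated as inevaluable they leave the denominator. Both choices raise the fraction. Section 11.3 says the fraction may inform later trials. There is no control arm, and Section 6.2.9 rules out independent review of responses, so nothing else in the plan would settle the classification.

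**Working it through.** **Is the second scan required?** For a first PD, no. The confirmation rule appears in Sections 6.2, 6.2.4 (note), 6.2.5 (note), 6.2.6 and 6.2.7. The obligation to scan is stated only for responses. Footnote 14 of the Study Calendar speaks of a confirmatory scan conditionally. Footnote 17 provides one confirmatory visit, at Week 52, triggered by Week 48.

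**Which category applies to growth of 20% or more at the first restaging with no later scan?**

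| Place | What it says | Points to |
|---|---|---|
| Table 2, SD row, with modified irRC PD needing confirmation | "Neither partial response nor progressive disease" | SD, as the residual |
| Section 6.2.4, SD definition | Growth must be too small to qualify for PD | Not SD |
| Section 6.2.6, modified irRC overall-response table | SD ends below a 20% increase; the PD row assumes confirmation | Not SD, but not PD either |
| Section 6.2.6, measurable-disease table | PD row carries no confirmation interval | PD |
| Section 6.2.4, note | New lesions give an unconfirmed PD, with no best-response category attached | Undefined |

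Section 6.2.6 adds that the criteria differ from iRECIST in that iRECIST separates unconfirmed from confirmed PD. There is therefore no intermediate category to use.

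**Who is affected?** Best overall response is the best one recorded since the start of treatment. A patient with SD or a response documented before progressing already counts. Only patients with no earlier SD or response matter, in practice those with PD at the first restaging (Week 8).

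**Size.** The plan gives no expected rate, target or power for this endpoint, so there is no figure to reproduce. Inputs:

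- N = 30, the evaluable goal for each part (Section 3.1.2).
- S = 6 patients truly SD or better (assumed).
- k = 3, 6 or 9 first-scan progressors with no later scan (assumed).

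Formulas: counted as PD, S/N; counted as SD, (S + k)/N; dropped, S/(N - k). Intervals are exact (Clopper-Pearson) 95%.

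| k | Counted as PD | Counted as SD | Dropped |
|---|---|---|---|
| 3 | 6/30 = 20.0% (7.7-38.6) | 9/30 = 30.0% (14.7-49.4) | 6/27 = 22.2% (8.6-42.3) |
| 6 | 6/30 = 20.0% (7.7-38.6) | 12/30 = 40.0% (22.7-59.4) | 6/24 = 25.0% (9.8-46.7) |
| 9 | 6/30 = 20.0% (7.7-38.6) | 15/30 = 50.0% (31.3-68.7) | 6/21 = 28.6% (11.3-52.2) |

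Each patient counted as SD adds 1/30 = 3.3 points, or 1/60 = 1.7 points if the two parts are pooled.

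Now let S run from 3 to 9 (true rate 10% to 30%) with the same k. Counting as SD adds k/30, which is 10 to 30 points. Dropping adds from 3/27 - 3/30 = 11.1% - 10.0% = 1.1 points to 9/21 - 9/30 = 42.9% - 30.0% = 12.9 points.

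Adjuvant bladder patients in Part I need not have measurable disease. If they are left out, N falls below 30 and each patient weighs more.

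**The case against.** A reader might infer that the plan's definitions make an unconfirmed progressor SD, so that the rule itself turns failures into successes. The documents do not support that. The SD definition in Section 6.2.4 and the modified irRC overall-response table both rest on measured change, and growth of 20% or more fails both. Table 2 compares three sets of criteria and gives one generic SD row for all of them; it was not written as a rule for missing confirmation. This part of the objection stands. The defect is a conflict between definitions, not an assignment to SD.

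The path to a missing scan can also be overstated:

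- PD documentation could mean confirmed PD. That would remove the conflict for patients still on therapy. It does not help those already off therapy, for whom the same sentence makes scans optional.
- Clinically stable progressors may stay on therapy and would continue scheduled restaging. This narrows the group, but leaves in it the patients who are not stable.
- Rapidly progressing disease is excluded at entry (Section 2.2.1.3) or removed before vaccination (Section 3.5.3.6). This limits early progression without eliminating it.
- The note in Section 6.2.6 asks for every effort to document progression after discontinuation. It concerns symptomatic deterioration and is best effort only.

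Finally, the endpoint is secondary and descriptive, with no threshold or test. That is correct, and it limits the consequence to the accuracy of an estimate.

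**Conclusion.** The concern holds in limited form. The plan requires a second scan for PD, does not require that the scan be done, and gives conflicting categories for a first-scan progressor without one. It does not say that such a patient is SD.

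Counting these patients as SD or dropping them both push the SD-or-better fraction upward. On the assumed 20% true rate the result is 30-50% or 22-29% respectively. The true rate and the number of unconfirmed progressors are assumptions, so these figures show sensitivity and do not predict the bias. What follows from the plan's own N is the 3.3 points per patient counted as SD at N = 30.

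No power, error rate or primary result changes. The point should still be settled before analysis, because otherwise the reported fraction depends on a choice made after the data are seen.

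**What to change.** In Sections 6.2.6 and 11.3, state that first-documented progression with no later scan counts as PD for best overall response and for the SD-or-better fraction. Apply the confirmation rule only where a later scan exists. Define the denominator as all treated patients with measurable disease. Reconcile the optional-scan sentence in Section 6.2 with the confirmation requirement, including whether PD documentation means first or confirmed PD.

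The classification rule and the denominator take a few sentences of text and require no extra scans. The reported fraction will be somewhat lower, and a rare patient with pseudoprogression who is never rescanned would count as PD. A separate line for confirmed CR plus PR would be useful reporting, but it is optional and not part of the defect.
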